8.4.7 Pregnancy

Pregnancy itself is not regarded as an AE.

If there is a pregnancy during the study period the subject must continue to be followed within the study and the outcome of pregnancy must be reported even if the expected date of delivery occurs after study completion.

A pregnancy confirmed during the study period must be reported by the Investigator on a pregnancy report form immediately upon acknowledgement be submitted to the Sponsor according to contact details specified in section 8.4.5. The report can be prospective or retrospective. Follow-up shall be conducted to obtain outcome information on all prospective reports.

Cases that led to foetal distress, foetal death or a congenital abnormality or birth defect are to be regarded as SAEs and shall be reported on the exposure *in utero* report form to the Sponsor immediately but no later than 24 hours after the Investigators awareness. These events shall be handled as SAEs during data processing. Other complications during the pregnancy that are related to the pregnant woman and fulfils any serious criteria, such as pre-eclampsia requiring hospitalisation, shall be reported and handled as SAEs. Elective abortions without complications will not be reported as AEs.

8.4.8 Anticipated Adverse Events

After the injection some common injection-related reactions might occur with both products. These reactions include bruising, erythema, swelling, pain, tenderness and itching at the injection site. Typically these reactions start on the day of treatment and resolve spontaneously within one week after injection, as observed in the Chinese clinical study for Restylane and in consistent with international results for both products.

Refer to the Restylane Defyne IB for all anticipated AEs.

| | | |
|--|--|---------------------------|
|  GALDERMA | Title 43CH1627 Clinical Study Protocol | Doc id MA-34970 |
|--|--|---------------------------|

2018-01-15 10:39

Effective date:

Effective

Version: 3.0

8.5 Device Deficiencies

8.5.1 Definition of Device Deficiency

A device deficiency is defined as an inadequacy of a medical device with respect to its identity, quality, durability, reliability, safety* or performance.

Note: Device deficiencies include malfunctions, use errors, and inadequate labelling.

*Inadequacy of device safety refers to properties of the device which could have or have led to an AE.

8.5.2 Recording Instructions

When a device deficiency is discovered the Clinical Study Complaint Form in the eCRF will be completed by the Investigator. The type of complaint shall be described and injury to the subject or user or unintended exposure to study product shall be reported as applicable. If an injury has occurred, an AE module or a SAE Form should be completed following instructions in section 8.4. If no SAE was experienced as a result of the device deficiency the Investigator shall assess whether or not the device deficiency could have led to an SAE if:

- Suitable action had not been taken,
- Intervention had not been made or,
- Circumstances had been less fortunate

The Sponsor will also make the same assessment in the Clinical Study Complaint Form.

8.5.3 Reporting Device Deficiency

The Investigator will complete the Clinical Study Complaint Form to the Sponsor using the contact details specified in section 8.4.5. A device deficiency that led to a SAE and any device deficiency that could have led to a SAE shall be reported within 24 hours after the Investigator's awareness in accordance to section 8.4.5.

In order to fulfil regulatory reporting requirements, all deficiencies with the study product must be assessed by both the Investigator and the Sponsor to determine if it could have led to a SAE. This assessment will be documented in the Clinical Study Complaint Form.

If an SAE has resulted from a device deficiency or if either the Investigator or the Sponsor assesses that the device deficiency could have led to an SAE the event will be reported in accordance with Regulatory requirements, as applicable.

The deficient study product shall be kept, if applicable, by the study site until the QA complaints group has confirmed whether the product shall be returned to Sponsor for further study or if it can be destroyed at the study site.

9 Data Handling and Management

9.1 Data management

Data management based on GCP refers to the activities defined to achieve safe routines to enter clinical data information into a database, efficiently and avoiding errors. The data management routine includes procedures for handling eCRFs, database set-up and

| | | |
|--|---|----------------------------|
|  | 
Title 43CH1627 Clinical Study Protocol
 | 
Doc id MA-34970
 |
|--|---|----------------------------|

2018-01-15 10:39

Effective date:

Effective

Version: 3.0

management, data entry and verification, data validation, and documentation of the performed activities including information of discrepancies in the process. The data management process will be described in detail in the data management plan (DMP).

The database, the data entry screens and program will be designed in accordance with the CSP. Data validation will be performed by computerised logical checks and manual review. Drugs and events will be coded in accordance with World Health Organization (WHO) Drug and medical dictionary for regulatory activities (MedDRA) dictionaries as specified in the DMP. Safety data (SAE) in the clinical database will be reconciled against the data in the safety database.

When all efforts have been made to ensure that the data recorded in the eCRFs and entered in the database is as correct and complete as possible, the clinical database will be locked. Study data will be transferred to SAS datasets which thereafter will be write-protected. Statistical analyses will be generated in SAS using data from the locked datasets.

9.2 Electronic case report forms

An eCRF is required and shall be completed electronically for each screened subject (screening visit) and included subjects (subsequent visits).

The eCRF includes password protection and internal quality checks, such as automatic range checks, to identify data that appear inconsistent, incomplete, or inaccurate. Study data will be transcribed directly from the source documents, which are to be defined at each site before inclusion of the first subject.

Authorised study site personnel designated by the PI shall complete data collection. Appropriate training and security measures shall be completed with all authorised study site personnel prior to the study being initiated and any data being entered into the system for any subject.

The study data is the sole property of the Sponsor and shall not be made available in any form to third parties without written permission from the Sponsor. At the end of the study, electronic data are kept at the Sponsor and a copy (provided by the vendor) at the study site as part of the Investigator file.

Any delegation of collection of data shall be specified in a signature and delegation log.

9.2.1 Data entry

All data shall be entered in English. The eCRFs should always reflect the latest observations on the subjects participating in the study. Therefore, the eCRFs shall be completed within 5 working days after the subject's visit. The subject's identity must always remain confidential, i.e. the name and address of the subjects must not be registered in the eCRFs or in the database. The Investigator must verify that all data entries in the eCRFs are accurate and correct. If some assessments are not done, or if certain information is not available, not applicable or unknown, the Investigator shall indicate this in the eCRF. The Investigator shall electronically sign off the study data. By signing, the Investigator takes responsibility for the accuracy, completeness, and legibility of the data reported to the Sponsor in the eCRF.

| | | |
|--|--|---------------------------|
|  GALDERMA | Title 43CH1627 Clinical Study Protocol | Doc id MA-34970 |
|--|--|---------------------------|

9.2.2 The query process

The monitor shall review the eCRFs and evaluate them for completeness and consistency by 100%. Each eCRF shall be compared with the respective source documents to ensure that there are no discrepancies between critical data. All entries, corrections, and alterations shall be made by the PI or his/her authorised designee. The monitor cannot enter data in the eCRFs. Once study data have been submitted to the central server via the eCRF, corrections to the data fields will be audit trailed, meaning that the reason for change, the name of the person who made the change, together with time and date will be logged. Roles and rights of the site personnel responsible for entering study data into the eCRF shall be determined in advance. If discrepant data is detected during review of the data, either by the Sponsor or its representatives, the responsible data manager or monitor shall raise a query in the electronic data capture application. The query shall state the question or data to be changed and shall be resolved in the system by the PI or his/her authorised designee. The appropriate study site personnel shall answer the queries in the eCRF. This will be audit trailed by the electronic data capture application meaning that the name of study site personnel, time, and date is logged.

9.2.3 User identification

Electronic CRF records will be automatically appended with the identification of the creator, by means of their unique User ID. Specified records shall be electronically signed by the Investigator to document his/her review of the data and acknowledgement that the data are accurate. This will be facilitated by means of the Investigator's unique User ID and password; date and time stamps will be added automatically at time of electronic signature. If an entry in an eCRF requires change, the correction shall be made in accordance with the relevant software procedures.

9.2.4 Audit trail

All changes will be fully recorded in a protected audit trail and a reason for the change shall be stated. Once all data have been entered, verified, and validated, the database will be locked.

9.3 Source documents

The eCRF is essentially considered a data entry form and does not constitute the original (or source) medical records unless otherwise specified. Source documents are all documents used by the Investigator or hospital that relate to the subject's medical history, that verifies the existence of the subject, the inclusion and exclusion criteria, and all records covering the subject's participation in the study. They include photographs, memoranda, material dispensing records, subject files, etc.

The PI is responsible for maintaining source documents. These shall be made available for inspection by the monitor at each monitoring visit. The Investigator must submit a completed eCRF for each subject for whom signed informed consent has been collected. All supportive documentation submitted with the eCRF, such as photographs, should be clearly identified with the subject number. Any personal information, including name, shall be removed or rendered illegible to preserve individual confidentiality.

| | | |
|--|--|---------------------------|
|  GALDERMA | Title 43CH1627 Clinical Study Protocol | Doc id MA-34970 |
|--|--|---------------------------|

Effective date: 2018-01-15 10:39

Effective

Version: 3.0

9.4 Record keeping and access to source data

The PI/institution shall permit study-related monitoring, audits and IEC review and shall provide direct access to the source data/medical record including the identity of all participating subjects (sufficient information to link records, i.e. eCRF, medical records, original signed Informed Consent Forms and detailed records of study product accountability). The records should be retained by the PI as required by local legislation and international guidelines. Any transfer of responsibility for storage of the records shall be documented and the Sponsor should be informed in writing.

The Sponsor shall verify that each subject has consented in writing to direct access to the original medical record/source data (by the use of written subject information and signed informed consent). The data recorded in the eCRFs shall be checked for consistency with the source documents/medical record by the monitor during monitoring (source data verification; SDV). In order to be able to perform SDV, information about each subject's participation in the study has to be detailed in the medical record.

The source data location log specifies what data that should be available in the medical record. The source data location log should also specify the data for which the eCRF serves as the source. Such data only need to be recorded in the eCRF and are typically associated with study-specific procedures and not with normal clinical care practice. For this type of study data the Investigator would not be expected to duplicate the information into the medical record.

9.5 Document and data retention

All records pertaining to the conduct of the study, including signed eCRFs, Informed Consent Forms, study product accountability records, source documents, and other study documentation must be retained after study completion according to national legislation and the CTA. Sponsor will inform the sites as to when these documents no longer needs to be retained. Measures should be taken to prevent accidental or premature destruction of these documents (e.g. protection against damage and unauthorised access, preferably by storage in a fire-proof cabinet). Refer to the CTA.

After study completion and database lock, a security sealed CD with electronic study data shall be provided by the eCRF vendor for archiving.

It is the PI's responsibility to inform Q-Med AB in writing if the Investigator file is moved or if the responsibility for the documents is transferred to someone else

10 Statistical Methods

10.1 General

A comprehensive Statistical Analysis Plan (SAP) with detailed description of all statistical analyses will be written and finalized prior to database lock (DBL). All statistical analyses, including summary tables and data listings, will be performed using the SAS® system (version 9.4 or later).

 Title **43CH1627 Clinical Study Protocol** Doc id **MA-34970**

Effective date: 2018-01-15 10:39

Effective

Version: 3.0

Continuous variables will be summarised using standard statistical measures, such as mean, median, standard deviation, minimum and maximum values. Categorical variables will be presented in frequency tables with number and percent of observations for each level.

All confidence intervals will be two-sided and use the 95% confidence level. All statistical testing will be two-sided and performed at a significance level of 5%.

10.2 Analysis Populations

The following populations will be defined:

- Safety Includes all subjects who were treated with Restylane Defyne or randomized to no-treatment group. Subjects are analyzed based on the as treated principle.
- Full Analysis Set (FAS) Includes all subjects who were treated with Restylane Defyne or randomized to no-treatment group. Subjects are analysed according to the randomisation assignment.
- Per Protocol (PP) Includes all subjects in FAS that comply to the protocol procedures with no deviations that can affect the evaluation of the primary variable.

The FAS population is the primary population for all effectiveness analyses. All safety analyses will be based on the Safety population.

10.3 Demographics, baseline assessments, and subject characteristics

Demographic endpoints and subject characteristics will be presented by treatment group using descriptive statistics.

10.4 Effectiveness Analysis

Primary analysis

The percentage of responders (a responder will be defined as a subject with at least 1 point improvement from baseline GCRS) will be calculated for Restylane Defyne group at 6 months after last treatment, and for no treatment Control Group at 6 months after randomization based on the Blinded Evaluator's assessment. CCI

In addition, for each group the two-sided 95% confidence intervals around the estimates of the percentage of responders will also be calculated. CCI

CC1

Secondary analysis

The percentage of responders based on the GCRS will also be derived at all applicable follow-up visits for both the Blinded Evaluator's assessment and the Treating Investigator's

| | | |
|--|--|---------------------------|
|  GALDERMA | Title 43CH1627 Clinical Study Protocol | Doc id MA-34970 |
|--|--|---------------------------|

2018-01-15 10:39

Effective date:

Effective

Version: 3.0

assessment respectively. The response rates and their 95% confidence interval will be presented by visit and group.

CCI

10.5 Safety Analysis

CCI

A graph will be generated to illustrate the incidence over time. Number of days with the event will be summarized using mean, SD, min, max and median.

All AEs will be coded by preferred terms in the MedDRA dictionary.

Related AEs will be summarised by SOC, PT and intensity. In addition, for related AEs the number of days to onset and the duration of event will be summarised by SOC and PT and treatment using mean, SD, min, max and median.

Serious AEs will be listed.

Non-related AEs will be summarised by SOC, PT, and intensity and by treatment.

10.6 Handling of Missing Data

Number of missing values will be summarized and reported as appropriate.

Different assumptions regarding the missing data will be used. For the primary effectiveness analysis, missing values in the FAS will be assumed to be missing due to lack of effect. Therefore missing data up to the Month 6 visit will be imputed using the baseline observation carried forward (BOCF) method. As an alternative approach, missing data will be assumed to be unrelated to treatment effect. CCI

More details will be given in the SAP. Both of these alternatives will estimate the effectiveness of the treatment policy (irrespective of use of unallowable treatments, procedures, or medications) rather than the true, clinical treatment effect.

To obtain an estimate of the true clinical treatment effect, the primary effectiveness analysis will be performed using the PP.

All other endpoints will be analysed on available data, i.e. no imputations will be done.

| | | |
|--|--|---------------------------|
|  GALDERMA | Title 43CH1627 Clinical Study Protocol | Doc id MA-34970 |
|--|--|---------------------------|

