2.2 Analysis Populations

The following populations will be defined:

- Safety Includes all subjects who were treated with Restylane Defyne or randomized to no-treatment group. Subjects are analyzed based on the as treated principle
- Full Analysis Set (FAS) Includes all subjects who were treated with Restylane Defyne or randomized to no-treatment group. Subjects are analyzed according to the randomization assignment.
- Per Protocol (PP) Includes all subjects in FAS that comply to the protocol procedures with no deviations that can affect the evaluation of the primary variable

The FAS population is the primary population for all effectiveness analyses. All safety analyses will be based on the Safety population.

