2.3.2 Withdrawals and Protocol deviations

All withdrawn subjects will be listed individually, including at least subject number, date and reason for withdrawal, and last visit performed. Subjects with CSP deviations will be listed individually, including subject number and observed deviation. Depending on the seriousness of the deviation, subject might be excluded from the PP population, which shall be documented prior to database lock.

 GALDERMA	Title Statistical Analysis Plan 43CH1627 - Chin	Doc id MA-38115
--	---	---------------------------

For this study, the protocol deviations that will exclude subjects from PP are identified (but not limited to) in Table 3 below.

Table 3. Protocol deviations

	Deviation
GENERAL	
	Visit out-of-window
	* Follow-up at Month 6 after last treatment performed earlier than 1 week before or later than 2 weeks after the scheduled visit for the treatment group
	* Follow-up at Month 6 after randomization performed earlier than 1 week before or later than 2 weeks after the scheduled visit for the control group
EFFECTIVENESS	
	Primary effectiveness endpoint
	* Pre-treatment GCRS by blinded evaluator not done
	* GCRS by blinded evaluator missing at Month 6 after last treatment for treatment group
	* GCRS by blinded evaluator not done at Month 6 after randomization for control group
	Treatment
	* Wrong treatment given at baseline
OTHER	
	Inclusion/exclusion criteria
	* Violate any inclusion or exclusion criteria considered to have substantial effect on the primary effectiveness endpoint
	Concomitant medication/procedures
	* Take any prohibited concomitant medication/procedures considered to have substantial effect on the primary effectiveness endpoint

Deviations from the SAP will be documented in the CSR.

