2.4.2 Handling of missing data

Number of missing values will be summarized and reported as appropriate. The baseline observation carried forward (BOCF) method will be used as the primary method to handle missing data on the primary effectiveness variable at the Month 6 visit in the FAS analysis set. This strategy is a conservative approach as it treats subjects with missing data as non-responders. Impact of missing data on the primary analysis for Month 6 endpoint will be evaluated by performing sensitivity analysis based on the PP population. In addition, missing data for the primary analysis will also be handled using the hot deck method.

All other endpoints will be analyzed on available data, i.e. no imputations will be done.

CCI

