2.4.3 Primary effectiveness analysis

The responder rate will be calculated for each group at Month 6 (after last treatment in Treatment Group and after randomization in Control group) based on the blinded evaluator's assessment. The responder rate in the Treatment Group will then be compared with the responder rate in the Control Group using a Fisher's exact test at a significance level of 5%. In addition, for each group the two-sided 95% confidence interval around the estimates of the percentage of responders will also be calculated. The treatment will be deemed a success if the p-value for the treatment difference on the primary endpoint is less than 0.05.

In order to assess robustness of the conclusions of the primary endpoint analysis, a logistic regression will be utilized, including baseline GCRS and treatment group as factors. The overall treatment effect will be used for assessing the robustness of the result of the primary analysis when corrected for baseline GCRS.

In addition, to obtain an estimate of the true clinical treatment effect, the primary analysis will be re-run using the PP analysis set.

 GALDERMA	Title Statistical Analysis Plan 43CH1627 - Chin	Doc id MA-38115
--	---	---------------------------

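### The Per Protocol analysis is labelled as the true clinical effect and reused as a missing-data check, but it is a subset selected largely after randomization and supports neither use

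*Protocol*

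**What the plan says.** Protocol 10.6 gives the PP run its purpose: "To obtain an estimate of the true clinical treatment effect, the primary effectiveness analysis will be performed using the PP". SAP 2.4.3 has the same: "In addition, to obtain an estimate of the true clinical treatment effect, the primary analysis will be re-run using the PP analysis set". Just before its sentence, the protocol says that both FAS approaches estimate a treatment-policy effect, whatever prohibited treatments were used, and not the true clinical effect.

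Protocol 10.6 also sets the missing-data assumptions. For the primary analysis, "missing values in the FAS will be assumed to be missing due to lack of effect", handled by baseline observation carried forward (BOCF). As an alternative, "missing data will be assumed to be unrelated to treatment effect". SAP 2.4.2 says of BOCF: "This strategy is a conservative approach as it treats subjects with missing data as non-responders".

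SAP 2.2 defines PP: "Includes all subjects in FAS that comply to the protocol procedures with no deviations that can affect the evaluation of the primary variable". Table 3 in SAP 2.3.2 lists deviations that remove a subject. One is "GCRS by blinded evaluator missing at Month 6 after last treatment for treatment group", with a matching line for the control group. The list is expressly not exhaustive. The note to Table A 18 says that the PP analysis uses complete data only, without imputation.

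SAP 2.4.2 then gives PP a second role: "Impact of missing data on the primary analysis for Month 6 endpoint will be evaluated by performing sensitivity analysis based on the PP population". It also plans a hot-deck imputation, reported in the FAS in Table A 19.

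**The concern.** Most of what decides PP membership happens after randomization, and some of it is a matter of judgement. Only the evaluator is blinded (Protocol 4.4.2). Exclusions must be documented before database lock, but neither document says that they are decided without knowledge of group. A comparison of two such subsets is not protected by randomization, so calling it the true effect claims a property that it lacks.

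The second role raises a separate problem. If the PP and FAS results differ, the difference could come from missing ratings or from any other exclusion, so PP does not isolate the impact of missing data.

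At stake is what a report meant to support registration in China (Protocol 2.5) may claim. It would carry two results for the primary endpoint, with the selected one described as true.

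**Working it through.** **1. The plan's own figures.** Protocol 10.10 and SAP 2.7 give 111 and 37 subjects after allowing for 15% drop-out. 111 + 37 = 148 and 111/37 = 3.0, as stated. At 15% loss, 111 × 0.85 = 94.35 and 37 × 0.85 = 31.45 remain. The assumed responder rates and power are redacted, and the plan gives no figure for the gap between PP and FAS, so there is nothing further to reproduce.

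**2. PP exclusions against the two uses of PP.**

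| Exclusion in SAP Table 3 | Concerns prohibited treatment? | Concerns a missing Month 6 rating? |
|---|---|---|
| No Month 6 Blinded Evaluator rating | no | yes |
| Month 6 visit out of window | no | no |
| No pre-treatment Blinded Evaluator rating | no | no |
| Wrong treatment at baseline | no | no |
| Eligibility violation judged important | no | no |
| Prohibited medication or procedure judged important | yes | no |

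One row matches the contrast that Protocol 10.6 draws with treatment policy. A different row matches the missing-data question. PP applies all six together, so it isolates neither.

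**3. Size of the missing-data part alone.** Suppose r of n randomized subjects in an arm respond, a share m has no Month 6 rating, and PP excludes nobody else.

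- FAS rate with BOCF = r/n
- PP rate = r/[n(1 − m)]
- ratio PP/FAS = 1/(1 − m)

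This gives 1/0.95 = 1.05, 1/0.90 = 1.11, 1/0.85 = 1.18 and 1/0.80 = 1.25 at 5%, 10%, 15% and 20% missing. It takes PP responders over PP subjects. The note to Table A 18 names the FAS as denominator, which I read as carried over from Table A 17.

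**4. Worked example.** Assumed: 17 of 111 and 6 of 37 missing; response among observed subjects about 70% and 10%, that is 66 of 94 and 3 of 31.

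| | Treatment | Control | Difference |
|---|---|---|---|
| FAS, BOCF | 66/111 = 59.5% | 3/37 = 8.1% | 51.4 points |
| PP, missing-data exclusions only | 66/94 = 70.2% | 3/31 = 9.7% | 60.5 points |

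With the same missing counts, and assumed observed rates of 50% to 90% (treatment) and 5% to 20% (control), the PP difference exceeds the FAS difference by about 4.5 to 13 points. The Fisher p-value in the FAS stays below 0.05 throughout that grid; the largest is 0.0051.

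**5. Where the formula stops.** If PP removes b further subjects, a of them responders, its rate becomes (r − a)/[n(1 − m) − b]. These extra exclusions lower the rate whenever a/b exceeds r/[n(1 − m)], so the net direction is not known in advance. If missingness is instead unrelated to outcome, the factor 1/(1 − m) measures how far BOCF understates the rate, not how far PP overstates it.

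**6. Is there a clean observed-case result?** For the Month 6 Blinded Evaluator responder rate, Table A 17 uses BOCF, A 18 is PP and A 19 uses hot deck. Table A 23 has a column for non-missing values, but its note says that Month 6 is imputed. None of the tables that can be read gives the FAS with only the missing ratings dropped.

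**The case against.** The strongest reply is that Protocol 10.6 announces more than one missing-data assumption. The lack-of-effect assumption belongs to the primary FAS analysis, and a complete-case run fits the alternative. A reader might infer that the plan contradicts itself by dropping from PP the very subjects it takes to be failures. The documents do not support that: varying the assumption is what sensitivity analyses are for. What remains is that the assumption PP needs is not stated for PP.

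Read in context, the label seems to mean the effect without prohibited treatments. That is fair as to intent, but PP also removes subjects for reasons unrelated to prohibited treatment.

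A reader might also infer that the whole missing-data check is confounded with compliance. It is not. Table A 19 repeats the primary analysis in the FAS with hot-deck imputation and no deviation exclusions. If donors come from the same arm, which the readable text does not say, its result should lie close to an observed-case one. Table A 6 lists the deviations affecting PP by category, so a reader could partly separate the reasons. These points reduce the problem, but they do not make PP a suitable missing-data check.

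Finally, FAS is already the primary population for effectiveness (Protocol 10.2, SAP 2.2), and SAP 2.4.3 ties success to the primary-endpoint p-value. That stands in full.

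**Conclusion.** The label is unsupported and PP is a poor missing-data check. Both matter for how supportive results are read. Neither touches the primary FAS test with BOCF.

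The factors 1.05 at 5% and 1.18 at 15% are illustrations. They require every missing subject to be a non-responder and no other PP exclusions. The 15% is a planning drop-out figure given without time point or arm, so Month 6 missingness may differ from it. The responder rates in the example are assumptions, because the sponsor's are redacted. A reader might infer that every PP rate will be 18% too high, or that PP must be the larger figure. The documents establish neither, since the other exclusions can remove responders.

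**What to change.** - **Protocol 10.6 and SAP 2.4.3:** delete the wording that presents PP as the true clinical treatment effect. Call PP a supportive analysis of protocol deviations and name the FAS result as the reported effect.
- **SAP 2.4.2:** replace PP as the missing-data check with an observed-case FAS row that drops only subjects without a Month 6 Blinded Evaluator rating. Show it beside Tables A 17 and A 19, and keep the hot-deck analysis.
- **Table A 18:** keep it as the deviation check, and correct the denominator in its note to the PP population.

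The cost is a few edited sentences, one corrected note and one extra row. The sponsor gives up presenting the PP figure as the true effect.
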